If we experience technical difficulties with the MRI scanner we may ask the participant to return to repeat appropriate study measures and the MRI scan and we would compensate accordingly.

In order to provide flexibility to study participants who may not be able to attend an appointment on the exact date of the protocol, we will allow some flexibility for scheduling appointments, but the window between Scan Days will be at least 2 days. If a participant misses a study Scan day due to illness or other unforeseen factors, s/he will be rescheduled as soon as possible. Because this population is typically unstable and often misses appointments, we expect scheduling difficulties and missed appointments to occur frequently. Research staff will work with participants to support their attendance. The maximum allowed time between the Screening Visit and the T1 Scan is 10 weeks. If a study participant goes beyond this time frame, then he or she will need to be reconsented. Also, any assessments required to establish eligibility and medical stability for the study will need to be repeated. Tasks for which the PI

believes there is no scientifically valid reason to repeat (e.g., WRAT or Baseline Neuropsychiatric Testing) will not be repeated.

Structural and Functional MRI Protocol:

Implementation: The neuroimaging protocol will be carried out at DHMC and UVM, overseen by our lead neuropsychologist. Our laboratory includes a "smoking hood", which allows for cannabis smoking in the scanner room and venting of smoke outside the laboratory. Within the scanner, participants will undergo a resting state scan, and the MID task, Paced Motor task, Aterial Spin Labeling (ASL), and (only at T1) a structural scan.

FMRI Imaging Parameters: MRI is a well-known noninvasive procedure typically used to image neuroanatomical structures. This is accomplished via the use of a high magnetic field and high frequency radio waves passing through the brain.

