RSC and Data Processing: Participants will be asked to lie in the scanner for approximately 8 minutes with eyes open, maintaining fixation,¹⁹² trying to not think of anything in particular, and not fall asleep.¹⁹³ It has been recently demonstrated that artifacts from participant motion result in substantial and structured changes in RSC data *despite* standard compensatory spatial registration and regression of motion estimates from the data.¹⁹⁴⁻¹⁹⁶ Quality Assurance (QA) procedures will be implemented to detect outliers in global signal intensity and motion time series with artifact mitigation software, with the identified outliers subsequently treated as confounds in the first level Generalized Linear Model (GLM.) Physiological sources of noise will be estimated and also treated as confounds. Anatomical volumes will be segmented into grey matter, white matter, and cerebrospinal fluid (CSF) areas. The time series characterizing estimated participant motion, as well as the blood oxygen level dependent (BOLD) time series within the participant-specific white matter mask and CSF mask, will be used as temporal covariates and removed from the BOLD functional data using linear regression, and the resulting residual BOLD time series will be band-pass filtered. Correlation maps will be produced by extracting the residual BOLD time course from seed regions, and computing correlation coefficients between that time course and the time course of all other voxels. Correlation coefficients will be converted to normally distributed scores to allow for second-level GLM analyses. We will assess RSC of the BRC using anatomically defined seed regions of interest (ROIs) (e.g., bilateral nucleus accumbens) defined by the literature.^{4, 91}

MID Task: Participants will complete an event-related fMRI MID task similar to that used in numerous studies of healthy participants,^{83, 166, 198} patients with SCZ^{4-8, 71, 72} and in our preliminary studies. Prior to scanning, instructions and the opportunity for a practice trial will be provided. In the scanner, visual stimuli will be presented electronically (e.g. through an MR-compatible goggle system) and response recorded electronically through an MR-compatible button response system. During the task, the participant is shown cues that indicate how much money can be won or lost on a given trial. This is followed by a fixation point of variable interval (estimated range of delay is 3000-7500ms) and then a square target

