3. Pharmacological treatment for addiction (e.g., disulfiram, naltrexone, acamprosate, topiramate, varenicline, bupropion) as determined by a study physician's review
4. Mental retardation
5. History of head injury with period of unconsciousness or focal brain injury as determined by a study physician's review
6. Metal objects within the body that would contraindicate an MRI
7. Pregnancy or currently nursing

8. Is deemed inappropriate for the study by the PI (e.g., due to other medical conditions, medication, psychiatric concerns, or other circumstances that could cause safety concerns or impair the person's ability to participate in the study.)

9. History of a seizure disorder as determined by a study physician's review
10. Is assessed as being suicidal or violent as determined by a study physician's review.
11. Has a legal guardian.
12. Any condition that would contraindicate use of cannabis or dronabinol.

Group 8 – Healthy control participants

1. Any Axis I psychiatric diagnosis (caffeine dependence is allowed)
2. Taking any psychotropic medication
3. Pharmacological treatment for addiction (e.g., disulfiram, naltrexone, acamprosate, topiramate, varenicline, bupropion) as determined by a study physician's review
4. Mental retardation
5. History of head injury with period of unconsciousness or focal brain injury as determined by a study physician's review
6. Metal objects within the body that would contraindicate an MRI
7. Pregnancy or currently nursing

8. Is deemed inappropriate for the study by the PI (e.g., due to other medical conditions, medication, psychiatric concerns, or other circumstances that could cause safety concerns or impair the person's ability to participate in the study.)

9. History of a seizure disorder as determined by a study physician's review
10. Current tobacco smokers
10. Is assessed as being suicidal or violent as determined by a study physician's review.
11. Has a legal guardian.

Note: Since the overwhelming majority of patients with SCZ smoke cigarettes (as do many with CUD), we will allow participants in Groups 1 – 7 to be tobacco smokers and we will control for smoking in our data analysis (see below). We exclude current tobacco smoking in the normal control participants since the fact of cigarette smoking could select participants with a dysregulated BRC as a basis for their cigarette smoking.

6. Financial Considerations:

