Aim 1 (Time 1 Group Differences): To determine whether at T1 dual diagnosis patients with SCZ-CUD (G1 - G3 combined) show (as compared to normal controls, G8):

- reduced fMRI activation of BRC (particularly the nucleus accumbens) to anticipation of monetary reward, as determined via group mixed effects ANOVA on contrasts of interest (e.g., anticipating reward > anticipating no reward);
- decreased resting state connectivity within the BRC as evaluated using the Statistical Parametric Mapping Version 8 (SPM8) mixed effects ANOVA on the Fisher-transformed r value connectivity maps derived from the nucleus accumbens seed ROI; and
- impaired reward responsiveness as determined using mixed effects ANOVA on response bias scores.

In addition, we will use a group mixed effects ANOVA to explore whether they will also differ from control participants with SCZ alone (G4) and control participants with CUD alone (G5, G6 and G7) on these measures.

Aim 2a and 2c (Group by Time effects on MID and BRC related to cannabis or dronabinol): Below, we describe the analyses involving dual diagnosis patients given cannabis (Group 1 -- G1); the same pattern of analyses will be carried out for the patients given dronabinol (Group 2 -- G2). Similar analyses will also be carried out for participants with CUD alone (Groups 5, 6 and 7 – G5, G6 and G7).

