The two sets of intervention effects (specific to SCZ-CUD and CUD alone) will be compared. To determine whether the dual diagnosis patients given cannabis (G1) will show differential changes in fMRI activation in specific ROIs within BRC and in RSC within the BRC between T1 and T2, we will first conduct a Group (G1, G3, G4, G7, G8) by Time (T1, T2) mixed-model repeated measures ANOVA. Predicting a significant omnibus ANOVA, we will next examine planned contrasts to address specific hypotheses: To determine whether cannabis ameliorates BRC dysfunction, we will compare brain activation/connectivity in the patient group given cannabis (G1) to that of the control groups (SCZ-CUD placebo [G3]); (SCZ alone [G4]; CUD alone placebo [G7]; and normal controls [G8]) using a Group (G1, G3, G4, G7, G8) by Time (T1, T2) mixed-model ANOVA followed by pairwise comparisons. The inclusion of Group 4 in this analysis will allow us to examine whether any significant cannabis effect on BRC in Group 1 (G1) is independent of any changes due to repeated testing specific to having a diagnosis of SCZ. Lastly, although not a primary hypothesis of interest, to further explore any potential placebo effect on BRC, we will also conduct a comparison of G3, G4, G7 and G8.

Aim 2b and 2c (Group by Time effects on RR related to cannabis or dronabinol): To explore whether the patients with SCZ-CUD who received cannabis (G1) will show differential changes in RR between T1 and T2 relative to G3, G4, G7 and G8, we will proceed as above for Aim 2a to assess response bias, and analogously for participants who received dronabinol (G2). Similar analyses will be used for Groups 5, 6, 7 and 8, with results compared to those obtained for patients with SCZ-CUD.

Although not aims of the study, we will assess the relationship between THC plasma levels and changes in BRC activation/connectivity following cannabis (G1 or G5) and dronabinol (G2 or G6) using covariance modeling in SPM8; we will conduct analyses to determine whether cannabis (G1 or G5) and dronabinol (G2 or G6) have comparable effects on fMRI BRC activation/connectivity using a Group (G1 or G5, G2 or G6) by Time (T1, T2) mixed-model ANOVA; and we will use cerebral blood flow values obtained from arterial spin labeling MRI as covariates in the ROI analyses of BOLD data to control for any artifactual changes in fMRI signal related to drug-induced influences on CBF.

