Diagnosis: We will do an all-source Structured Clinical Interview for DSM-IV-TR (SCID)¹⁵⁷ to ensure each participant meets the appropriate diagnostic criteria for his or her group. Use of the DSM-IV will allow us to have a consistent measure across both the previous pilot study and this one (and the DSM-5 SCID is not yet available). The SCID-II module for Antisocial Personality Disorder will be used to detect whether or not participants meet criteria for this disorder. Research suggests that trauma may change reward circuitry. We will therefore track trauma exposure using the PTSD Screening Questionnaire and use these data as covariates in our final analyses.

Substance Use: We will use the Timeline Follow-Back (TLFB) calendar to establish use of cannabis or other substances following the recommended method of Sobell.¹⁷³

Psychiatric symptoms: We will use the PANSS (Positive and Negative Syndrome Scale)¹⁷⁴ to assess psychiatric symptoms, as well as positive and negative symptoms. The Barkley Adult ADHD Rating Scale-IV (BAARS-IV; Barkley, 2011) will be administered during the Baseline Neuropsychiatric Testing visit to assess current symptoms of attention deficit.

Neurological symptoms: Extrapyramidal system effects will be assessed with the Simpson-Angus Scale (S-A),¹⁷⁵ the Abnormal Involuntary Movements Scale (AIMS),¹⁷⁶ and the Barnes Akathisia Scale.¹⁷⁷

Cannabis-related effects: We will employ a brief version of the visual analogue self-report scale (VAS) used by our consultant, [name], in her studies of cannabis use.^{14, 178, 179} The VAS will be used to rate mood, "high" and "liking". The Cannabis Withdrawal Assessment Scale will be utilized at each visit while participants are establishing abstinence from cannabis.

Cannabis craving: The 12-item self-report Marijuana Craving Questionnaire (MCQ-12) will be used to rate craving for cannabis.^{180, 181} We will use the total score for our analyses.

Intellectual Functioning: Study participants will complete the Wide Range Achievement Test – 4 (WRAT-4) reading subtest¹⁸³ at screening as an estimate of premorbid intellectual functioning.

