Information gathered through interviews will be coded to a study number. The name-number code will be kept by the PI and interviewers in a locked file cabinet. Coded interviews will be kept in separate locked cabinets in research offices at the offices of the Psychopharmacology Research Group (PRG) and the scanning laboratories at DHMC and UVM.

Data will be managed according to usual procedures of the PRG and neuropsychology research groups and UVM. These procedures include careful editing and coding of interviews and other research forms prior to data entry; locked storage of original data forms at the PRG; storage of scanning data on password protected computers, software controls on all data access; and regular backup of data files. Neuropsychological testing data and imaging data sent to DHMC from UVM will be encrypted and sent securely

We have obtained a certificate of confidentiality. Additionally, the Geisel School of Medicine at Dartmouth's Department of Psychiatry is a HIPAA covered entity, so we follow those federal privacy regulations in addition to our current confidentiality safeguards.

All imaging study data are labeled with a unique study ID and the date of acquisition. The link between participant information and the study ID is kept in a locked file cabinet, within a locked office, and will only be accessed by study personnel. Coded data is recorded in a database, password protected on a secure server in the Brain Imaging Lab, Psychiatry. Images are transferred to the Brain Imaging Laboratory from the Advanced Imaging Center at DHMC and archived using secure systems. Images and scan readings will become part of each

participant's permanent medical record and this is clearly outlined in the consent form and discussed with each participant during the consent process

d) Will data that identify individual subjects be published or in any way be disclosed to third parties other than project personnel?

Yes No *If yes, please explain here and incorporate the information in consent form:*

28. Responsibility for costs of injury or illness related to research:

Will the sponsor or other funding agency be responsible for costs of injury or illness related to the research?

Yes No

If applicable, describe whether or not the sponsor will be responsible for investigational device removal if required:

NA

If the sponsor or other funding agency will not be responsible for costs of injury or illness related to research, please complete:

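### Scans come from two centres, but the T1 group comparisons of MID activation and resting-state connectivity carry no scanner term and nothing balances the groups over scanners

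*Combined protocol and SAP*

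**What the plan says.** Two places establish that images come from two centres. Section 4 (Structural and Functional MRI Protocol, Implementation) states "The neuroimaging protocol will be carried out at DHMC and UVM, overseen by our lead neuropsychologist", and section 27c adds "Neuropsychological testing data and imaging data sent to DHMC from UVM will be encrypted and sent securely".

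Section 7b, Aim 1, compares the combined SCZ-CUD groups with healthy controls at T1. MID activation is assessed "as determined via group mixed effects ANOVA on contrasts of interest"; RSC is assessed by a "mixed effects ANOVA on the Fisher-transformed r value connectivity maps derived from the nucleus accumbens seed ROI". The same approach is used to explore differences from SCZ alone and CUD alone. No scanner or site factor is named in these models or elsewhere in section 7.

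Other nuisance variables are addressed. The note closing section 5 promises control for smoking. Section 7b says "we will use cerebral blood flow values obtained from arterial spin labeling MRI as covariates in the ROI analyses of BOLD data". Section 10 (Diagnosis) will track trauma exposure and "use these data as covariates in our final analyses". In section 4, motion, white-matter and CSF signals are "removed from the BOLD functional data using linear regression, and the resulting residual BOLD time series will be band-pass filtered". None of these is a scanner term, and no harmonisation, cross-scanner calibration or balancing of groups over scanners is described.

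**The concern.** MID activation and RSC are two of the three endpoints listed in section 7a. In Aim 1 they are compared between diagnostic groups, so randomisation gives no protection. If one scanner reads systematically higher and holds a larger share of one group, part of the scanner difference is counted as a reward-circuit deficit or hides one. A model with group alone cannot tell the two apart.

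Equal shares are not assured. The feasibility answer before section 18 draws SCZ patients from Dartmouth-affiliated sites and Groups 5 to 8 from advertising and flyers. Section 25f extends advertising to the SCZ groups but keeps clinic referral as an additional route for them only.

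The planned processing helps in part. The MID endpoint is a within-person contrast, so a constant baseline signal difference cancels. The RSC steps remove some noise. Neither removes a difference between scanners in gain or residual noise. The behavioural reward task is not an imaging measure and is outside this point.

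**Working it through.** **Inputs from the documents (section 7c):** 75 SCZ-CUD v 25 controls; d ≥ 0.7 detectable with at least 80% power; pilot effects of 1.10 (MID) and 0.84 to 1.28 (RSC).

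**Assumptions, because the documents are silent:** two-sided 5%; SD 1; a scanner offset that is constant and additive; 50% of controls at one centre. The offset and the patient share are varied.

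**Step 1: the plan's own figure.** SE = √(1/75 + 1/25) = 0.231. At d = 0.7 the noncentrality is 0.7/0.231 = 3.03; with 98 degrees of freedom, power is 85%. The statement of at least 80% reproduces.

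**Step 2: the bias.** Bias = offset × (patient share − control share at one scanner). With a 0.5 SD offset, 70% v 50% gives 0.5 × 0.20 = 0.10 SD, and 90% v 50% gives 0.5 × 0.40 = 0.20 SD. With equal shares it is zero for any offset.

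**Step 3: false positives (noncentral t, noncentrality = bias/0.231).**

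| Patients v controls at one centre | Bias (SD) | False positives |
|---|---|---|
| 50% v 50% | 0 | 5.0% |
| 60% v 50% | 0.05 | 5.5% |
| 70% v 50% | 0.10 | 7.1% |
| 80% v 50% | 0.15 | 9.9% |
| 90% v 50% | 0.20 | 13.8% |

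Allowing the offset also to inflate the residual SD gives 13.5% in the last row. A 0.2 SD offset at 70% v 50% gives 5.3%; a 0.8 SD offset at 90% v 50%, with SD inflated, gives 26%. A simulation with a different split (20% of patients v 60% of controls, 0.5 SD offset, bias 0.20 SD) gave 12.8%, and about 5% once scanner was in the model. In the exploratory comparison with CUD alone (75 v 75), false positives are 9.3% at 0.10 SD and 22.9% at 0.20 SD.

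**Step 4: power when the bias opposes the effect (d − bias in place of d).**

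| True d | No bias | 0.10 SD | 0.20 SD |
|---|---|---|---|
| 0.70 | 85% | 73% | 57% |
| 0.84 | 95% | 89% | 78% |
| 1.10 | 99.7% | 99% | 97% |

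A 0.20 SD bias in the other direction raises apparent power at d = 0.7 to 97% by overstating the effect. At 1.10 the test survives, but the estimate becomes 0.90 or 1.30, an error of 0.20/1.10 = 18%.

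**Step 5: with scanner in the model.** The SE is multiplied by 1/√(1 − r²), where r is the correlation of group with scanner. At 90% v 50%, the overall share is 0.75 × 0.90 + 0.25 × 0.50 = 0.80, so r² = (0.1875 × 0.40)²/(0.1875 × 0.80 × 0.20) = 0.1875 and the multiplier is 1.109.

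| Split | SE multiplier | Power at 0.7 | Power at 1.10 |
|---|---|---|---|
| 50% v 50% | 1.000 | 85% | 99.7% |
| 70% v 50% | 1.017 | 84% | 99.6% |
| 80% v 50% | 1.045 | 82% | 99.5% |
| 90% v 50% | 1.109 | 77% | 98.9% |

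**Step 6: gain instead of offset.** Suppose patients average 0 and controls 1.1 SD on the MID contrast, in line with the pilot (section 3 reports very little activation in patients). A scanner with relative gain 1 + g leaves patients at 0 and moves controls by 1.1g. A 0.5 SD shift in controls then needs g = 0.5/1.1 = 45%, and 0.8 SD needs 73%. The group difference is 1.1 on one scanner and 1.1(1 + g) on the other, so group and scanner interact, and a main effect for scanner only partly corrects this.

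**The case against.** The strongest case against is about mechanism and size. Once baseline shifts cancel in the MID contrast, what remains is mainly gain, while the illustration uses a constant offset. Step 6 shows that the 0.5 SD case is demanding for MID under pilot-like means. This stands: the figures are illustrative, and a scanner main effect alone is not a full remedy.

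Adjustment also has a price. In this set-up the scanner term increases the mean squared error of the group difference when the offset is below about 0.21 SD (70% v 50%), 0.23 SD (80% v 50%) or 0.28 SD (90% v 50%), because the variance it adds exceeds the squared bias it removes. That stands as a trade-off.

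It can also be said that section 7b is not a full covariate list, since smoking and trauma are promised elsewhere and not written into the Aim 1 models. That is true, but those two are at least promised somewhere; scanner is not.

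A reader might infer that Aim 1 will be biased, or that patients and controls are scanned at different centres. The documents support neither: they report no scanner difference and no counts per scanner, and advertising serves every group. Nor does the point show that the drug-effect contrasts are compromised. An additive offset cancels in the T1-to-T2 change if both scans use one scanner. The plan does not require this, but nothing says participants will switch, and the aim of comparable head positioning across sessions is consistent with a single magnet.

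**Conclusion.** The point holds as an unprotected risk in the T1 between-group comparisons of MID activation and RSC. Bias needs two conditions together, a systematic scanner difference and an uneven spread of groups, and the plan guards against neither.

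Under the stated assumptions, a net bias of 0.10 to 0.20 SD takes the false-positive rate from 5% to between 7% and 14%, and a bias of 0.10 SD against the effect is already enough to bring power at d = 0.7 under the plan's 80%. The exposure is greatest near d = 0.7 and at the lower RSC pilot effect of 0.84. At the pilot MID effect the test is robust and only the estimated size of the deficit is at risk. The upper figures (26%, and 22.9% in the exploratory comparison) come from the harsher assumptions and should not be read as expected rates. The change is worth making because it is cheap and because no later model can separate scanner from diagnosis if a group is scanned at one centre only.

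**What to change.** In section 7b, add scanner (DHMC/UVM) as a fixed factor to the T1 models of MID activation and RSC, for Aims 1a and 1b. Report counts by group and scanner. As a sensitivity check for gain differences, report the group-by-scanner interaction or the group difference within each scanner.

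In section 4, state that group proportions will be kept similar over the two scanners where feasible, with every compared group represented on both, and that each participant has T1 and T2 on the same scanner. The last condition is what protects the Group by Time contrasts from an additive offset.

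The analysis cost is one degree of freedom, with almost no power loss if the groups are balanced. Under strong imbalance (90% v 50%) the SE widens by 11% and power at d = 0.7 is 77%, below the plan's stated 80%; at the pilot MID effect it remains about 99%. Keeping proportions similar avoids that loss at the price of some scheduling effort.

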stimulus. Following the disappearance of the target, feedback is provided as to the amount of money won for correct responses to the target (responding while target is displayed). An incorrect response is also indicated. Feedback is followed by a variable inter-trial interval (ITI). Each cue is presented an equal number of times in a pseudo-randomized order. Following completion of the session, participants will be told that they won \$35 during the task (the amount is fixed at \$35 to ensure that all participants receive the same amount irrespective of performance capacity).

Pulsed Arterial Spin Labeling (PASL): Since it is not known if cannabis or dronabinol will induce neurovascular changes, we will use PASL²⁰³⁻²⁰⁹ to characterize resting regional cerebral blood flow (CBF) during each scan session.²¹⁰⁻²¹² ASL methods measure CBF by using water in arterial blood as an endogenous tracer.^{206, 213} PASL, which alternates control and labeling scans that are then compared to quantify perfusion,^{214, 215} will be implemented.²¹⁶ Derived perfusion images will be coregistered to the fMRI and anatomic scans and analyzed by tissue compartment and project-specific ROIs. Masks derived from segmented anatomic maps will be used to estimate global and local gray matter and white matter perfusion values. Perfusion will also be determined for the same ROIs targeted in the fMRI experiments.

fMRI Paced Motor Task (PMT): Participants will complete a visually-triggered sequential finger movement fMRI task in which periods of finger movement alternate with rest for a total of 8 minutes.

Structural MRI Imaging Parameters: Structural scans will be acquired during the baseline scan session only. We will also acquire survey images as a screen for focal lesions. T1-weighted anatomic reference images will be acquired in the same planes and thickness during each scan session. The magnet's repositioning system will be used to ensure comparable head positioning across the scan sessions.

Eye Camera: We will use an MRI-compatible camera with integrated LED infrared light (MRC Systems, Germany; model 12M-I) that can be used inside the bore of the scanner. This will allow us to monitor and record participant's eyes to determine whether they are keeping them open/closed per instructions during the scan session. The camera is based on a single light-emitting-diode (LED) which is embedded in the titanium housing and emits diffuse light.

GENETIC TESTING

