Common side effects: A "high" feeling (e.g. laughing easily, feeling happy, having a heightened awareness)

Occasional side effects (reported in 3-30% of people): Paranoia, confusion, nervousness, sleepiness, dizziness, stomach pain, nausea with or without vomiting, tachycardia, flushed face

Rare side effects (reported in less than 3% of people): Red eyes, diarrhea and/or incontinence, depression, nightmares, trouble speaking, visual problems, ringing ears, low blood pressure

Seizures have been reported in people taking dronabinol. Patients with a history of a seizure disorder will be excluded from this study.

Recruited patients with dual diagnosis and participants with CUD (without schizophrenia) will all be frequent cannabis users. Thus, we do not expect anything more than minimal effects from the modest dose of THC in the cannabis cigarettes or the two 7.5 mg dronabinol capsules. However, as with the potential of symptom exacerbation in the dual diagnosis patients (above), we will monitor all CUD patients until it is determined by an MD that they can be safely discharged and be prepared to act immediately to provide treatment and to maintain participant safety. Moreover, participants in Groups 1-3 and Groups 5-7 will have a baseline medical history and physical assessment to rule out medical contraindications to administration of dronabinol or cannabis. The assessment will include blood pressure, EKG, complete blood count and blood chemistry screen. All women in the study will have a pregnancy test as described in the section on assessments.

Risk Related to Confidentiality: This research involves monitoring and treatment of patients who use cannabis, an illegal substance. Participants may engage in other illegal activities. Maintaining confidentiality is an area of utmost importance for this population.

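### The Aim 1 resting-state comparison has no group-level motion term and no rule for the eye-closure recording, so residual differences in movement or wakefulness between patients and controls can bias it

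*Combined protocol and SAP*

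**What the plan says.** Section 4 (RSC and Data Processing) states that "artifacts from participant motion result in substantial and structured changes in RSC data" and that standard spatial registration and regression of motion estimates do not remove the problem. It then lists what will be done:

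- Outlying volumes are flagged automatically; the plan has the "identified outliers subsequently treated as confounds in the first level Generalized Linear Model (GLM".
- Noise of physiological origin is modelled in the same way.
- Motion, white-matter and CSF time series are regressed out of each participant's data before the correlation maps are computed.

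The resting scan lasts about 8 minutes, with eyes open and without sleep. Section 4 (Eye Camera) provides a recording "to determine whether they are keeping them open/closed per instructions during the scan session".

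Section 4 also schedules a "visually-triggered sequential finger movement fMRI task in which periods of finger movement alternate with rest". Only the structural scan is restricted to T1, so this task is run at both sessions.

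In Section 7b, the Aim 1 RSC analysis is a "mixed effects ANOVA on the Fisher-transformed r value connectivity maps derived from the nucleus accumbens seed ROI". Aim 2a uses Group by Time ANOVA. Elsewhere the plan names three adjustments: tobacco smoking (Section 5, closing note), trauma exposure (Section 10, Diagnosis), and cerebral blood flow from arterial spin labelling (ASL) in the ROI analyses of BOLD data (Section 7b, after Aim 2). No motion summary, eye-closure measure or motor-task analysis appears in Section 7b.

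**The concern.** Regressing motion within a run removes the signal that tracks that person's movement linearly. It does not make people who moved a lot comparable with people who moved little, and the protocol itself says that artefact remains after such regression. What remains can differ between groups. The usual remedy is a participant-level motion summary in the second-level model, and the plan has none. It also gives no threshold for excluding a run.

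Aim 1 is where this matters most. Patients and controls are not randomised, and any group difference in movement or wakefulness during the resting scan goes straight into the connectivity contrast. The camera would show who closed their eyes, but no rule turns the recording into an exclusion, a covariate or a sensitivity analysis. A connectivity difference could then be read as a reward-circuit deficit when part of it reflects scan behaviour.

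Aim 2a has a milder version of the problem. Randomised placebo (G3) protects the comparison of arms, but not the interpretation if the drug itself changes movement or alertness.

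**Working it through.** **The plan's own figure.** Section 7c states at least 80% power at d = 0.7 for 75 v 25. Alpha and sidedness are not given; I assume two-sided 5%. The noncentrality is d × √(n₁n₂/(n₁+n₂)) = 0.7 × √(75×25/100) = 0.7 × 4.330 = 3.031. Power is 85.1% by the noncentral t (85.8% by the normal approximation), so the stated figure is reproduced.

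**Where motion is handled.** Each remedy in Section 4 was checked for level. Outlier confounds, tissue and motion regression, and physiological noise all act within a participant. The second-level models in Section 7b contain Group, or Group and Time. Adding the covariates named elsewhere brings in smoking, trauma and, for ROI analyses, CBF. Motion and eye closure are in neither list.

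**Illustration of bias.** Let m be the standardised group difference in residual motion and r its within-group correlation with the connectivity value. Neither is in the documents; both are assumed. With no true effect, spurious d = m × r, and the rejection rate follows from the noncentral t with noncentrality 4.330 × d and 98 df.

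| m | r | spurious d | rejection, 75 v 25 |
|---|---|---|---|
| 0.3 | 0.2 | 0.06 | 5.8% |
| 0.3 | 0.3 | 0.09 | 6.7% |
| 0.5 | 0.2 | 0.10 | 7.1% |
| 0.5 | 0.3 | 0.15 | 9.9% |
| 0.8 | 0.2 | 0.16 | 10.5% |
| 0.8 | 0.3 | 0.24 | 17.7% |

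Over the same range of m, r = 0.1 gives 5.2 to 6.4% and r = 0.4 gives 8.1 to 27.9%. The calculation is for one uncorrected test of one connectivity value, not for a thresholded map.

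**Price of a motion covariate.** With p = 0.75 the share of patients, the squared correlation of group and motion is R² = m²p(1−p)/(1+m²p(1−p)), and SE = √[(1−r²)(1/75+1/25)/(1−R²)]. At m = 0.8 and r = 0.2:

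- R² = 0.12/1.12 = 0.107
- SE = √(0.96 × 0.0533/0.893) = 0.239
- noncentrality = 0.7/0.239 = 2.92
- power = 82.5% on 97 df

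Over m = 0.3 to 0.8 and r = 0.2 to 0.4, power runs from 82.5% to 90.1%. This is for one covariate; a second, correlated one costs one more degree of freedom and some further collinearity.

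**Motor task as a test of specificity.** For 25 v 25 at d = 0.7, noncentrality is 0.7 × √12.5 = 2.475 and power is 67.9%. A non-significant motor-cortex result would not show that no general BOLD change occurred.

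**The case against.** The plan does more than standard motion regression: the sentence about artefact is its reason for adding outlier detection and physiological noise modelling. Residual motion may therefore be small. At the low end of the illustration the error rate is 5.8% against 5%, and even the high-end d of 0.24 is about a third of the design effect of 0.7 and well below the pilot RSC effects of 0.84 to 1.28. This stands as a limit on size. It does not remove the gap, because the documents do not describe how motion was handled in the pilot, and nothing planned would reveal a residual difference.

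Adjustment can also overcorrect if movement is part of the illness. That is fair, and is the reason to report both models.

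Several stronger readings are tempting but unsupported:

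- *The RSC group model contains Group alone.* Smoking and trauma are planned covariates, although they are named outside Section 7b.
- *A general BOLD change under THC is uncontrolled.* ASL blood flow is a planned covariate in the ROI analyses. It is incomplete, because it is limited to ROI analyses and resting flow does not capture a change in neurovascular coupling. It is still a control. For the monetary incentive delay (MID) task, the reward minus no-reward contrast also cancels additive shifts, though not a change in gain.
- *Drug sleepiness threatens Aim 1.* Section 14 lists "Paranoia, confusion, nervousness, sleepiness, dizziness" among effects in 3 to 30% of people, but says these arose with regular dronabinol use and that the likelihood after one dose is unknown. T1 involves no drug.
- *Artefact would specifically lower connectivity.* The protocol speaks of structured change and gives no direction.
- *The motor task should decide whether a reward-circuit effect may be claimed.* The documents give the task no purpose, there is no criterion for a matching change, power is about 68%, and the task cannot test RSC specificity.

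**Conclusion.** The point holds for Aim 1 RSC. The protocol says that motion artefact survives standard correction, corrects only within participants, and then makes a non-randomised group comparison with no group-level motion term and no use of the eye recording. Bias is possible; its direction and size cannot be derived from the documents. The 6 to 18% rejection range rests wholly on the assumed r of 0.2 to 0.3 and motion difference of 0.3 to 0.8 SD, for one two-sided 5% test. Eye closure is not quantified.

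For Aim 2a the point is limited to reporting: the randomised drug contrast remains valid, and partial control of drug-related BOLD change is already planned. This is worth correcting before analysis because the remedy needs no new scans. It does not invalidate the design or the sample size.

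**What to change.** **Aim 1 RSC.** In the second-level model, add each participant's mean motion and number of flagged volumes, next to smoking and trauma. Report the group difference with and without the two motion terms. Add a sensitivity analysis that drops resting runs with eyes closed for more than a share of the 8 minutes fixed before unblinding or analysis.

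**Aim 2a.** Report post-dose motion and eye closure by arm, without adjusting for them, since the drug may cause both. Report the G1–G3 and G2–G3 difference in change of motor-cortex response to the paced motor task, with confidence intervals, as a supportive check on general BOLD change alongside the ASL covariate. Do not make the reward-circuit claim conditional on it.

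**Cost.** There is a small loss of precision from two covariates: on the assumptions above, Aim 1a power at d = 0.7 stays above 80% with one motion term. Some illness-related variance may be removed, hence both models. The eye recordings need a scoring method and time: 100 participants × 8 minutes is 800 minutes, about 13 hours of footage for Aim 1, and the T2 resting runs of G1 to G3 add 75 × 8 = 600 minutes, or 10 hours.
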